12.3. Vital signs

Vital signs (blood pressure, heart rate, temperature, and respiratory rate) are collected at

screening, baseline, and every two weeks thereafter according to the schedule in Exhibit 2 –

Exhibit 7. Weight is collected at screening and week 52 and will be included in the vital signs

summary. Vital sign values and changes from baseline will be summarized by study part,

treatment group and time point. Figures may be used if appropriate.

12.4.Physical examination

Physical examinations are planned at screening. The number and percentage of subjects with

an abnormal result for the latest pre-randomization examination will be summarized by study

part and treatment group for each body system examined. During the study, the number and

percentage of subjects with an abnormal result for each body system (change or no change

from the last examination) will be summarized by study part, treatment group and visit. If

more than one physical examination is performed for a subject at the same visit, the latest

examination will be used. Early withdrawal examinations will be assigned to the closest visit

at which an examination was scheduled to occur. The denominators will only include subjects

with a study visit being summarized.

CONFIDENTIAL

All physical examination abnormal results will be listed.

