n (%)	n (%)	n (%)	P-VALUE

Second, the results will be presented by treatment group, stratified by Part A vs. Part B. The layout will be presented similar to that shown below:

Part A	Part A	Part B	Part B
Sham	Treatment	Sham	Treatment
(N=X)	(N=X)	(N=XX)	(N=XX)
n (%)	n (%)	n (%)	n (%)

Additionally, all formal statistical analyses will be stratified by whether subjects were randomized into Part A vs. randomized into Part B.

For Part C, all table presentations will display results by path of entry (e.g., Part A/B Sham, Part A/B Treatment, Part C) and overall.

In addition to tabular summaries, all relevant electronic case report form (eCRF) data and external lab data will be provided in by-subject listings. All data listings, summaries, figures, and statistical analyses will be generated using SAS Version 9.4 or higher [3].

8.1.Study days

For the purpose of the analysis, the reference time (time zero) is defined as the start date/time of study drug administration for all purposes, except for the age and concomitant medication where time zero is the time when Informed Consent was granted. Randomization may occur on or before Study Visit 1 (Day 0). Protocol-defined Day 0 is the calendar date of the first administration of the study drug. Study day will be calculated relative to first administration of the study drug. Specifically:

Study day = date of visit/test/procedure – first dose date + 1.

Statistical analyses will be performed using study day as defined above. Protocol study day =

Study day if study day < 0; or (Study day - 1) if Study day ≥ 0 . All data listings will be based

on the Study day as defined above.

8.2.Baseline

The baseline value for all NPC-SS related endpoints will be based on the assessment

performed at screening. The baseline value for all other study assessments including but not

limited to vital signs, clinical outcome and disease progression measures, and concomitant

medications is defined as the last non-missing value prior to the first dose, unless otherwise

specified.

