Neurological examination ^f	X													X	
Clinical laboratory testing ^g	X							X						X	
12-lead ECG	X														
Audiologic testing	X	X	X#	X#	X#	X				X				X	
Auditory brainstem response	X					X#									

August 27, 2018 Page 50

Visit Number		1	2	3	4	5	6	7	8	9	10	11	12	13	14
Study Day	Day -45 to Day -1	0	14	28	42	56	70	84	98	112	126	140	154	168	182
Window (days)			(±3)	(±3)	(±3)	(±3)	(±3)	(±7)	(±7)	(±7)	(±7)	(±7)	(±7)	(±7)	(±7)
Time Point (Week)	Screening	1 st Study Dose	2	4	6	8	10	12	14	16	18	20	22	24	26
NPC Clinical Severity Intake	X	X				X				X				X	
Clinician-CGIC ^h and Caregiver-CGIC		X				X				X				X	
TUG Test		X				X				X				X	
9-Hole Peg Test		X				X				X				X	
EQ-5D-3L QoL		X				X				X				X	
Confirm subject eligibility		X													
Randomizationi		X													
Collect plasma biomarker samples ^j		X				X#		X						X	
Sham or lumbar puncture and study drug administration		X	X	X	X	X	X	X	X	X	X	X	X	X	X
Collect CSF samples (study drug subjects only)		X				X#		X						X	
Collect whole blood for genetic testing		X													
Adverse events ^k		X	X	X	X	X	X	X	X	X	X	X	X	X	X
Concomitant medications		X	X	X	X	X	X	X	X	X	X	X	X	X	X

CGIC = Clinical Global Impression of Change; CSF=cerebrospinal fluid; ECG = electrocardiogram; hx=history; NPC = Niemann-Pick disease, type C; NPC1=Niemann-Pick disease, type C1; QoL=quality of life; TUG=timed up and go

 $^{^{\}rm a}$ Medical history includes history of NPC1 disease, diagnosis date, and prior treatments.

^b Urine will be obtained for urinalysis and biomarker testing

August 27, 2018

Page 51

^c Full physical exam at Screening; abbreviated physical exam at all other visits.

 $^{^{}m d}$ Vital signs, including blood pressure, will be recorded following a 5-minute rest in supine position.

^e A second set of vital signs will be recorded following recovery of sedation from lumbar puncture or sham procedure.

 $^{^{}m f}$ Full, videotaped neurological exam at Screening and Week 52; brief, videotaped neurological exam at Week 24.

^g Clinical laboratory tests include chemistry, hematology, and coagulation.

^hBlinded Clinician to meet with subject and assess overall status and functionality that will form baseline for future Clinician-CGIC assessments.

ⁱ Randomization may occur on or before Study Visit 1, Day 0, after receipt of NPC Clinical Severity Score from central rater to confirm eligibility.

^j Plasma samples for biomarkers should be obtained prior to intrathecal or sham treatment.

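### SAP 12.4 compares each on-study physical exam with the previous exam and plans no shift from the pre-treatment exam, so later-visit tables cannot separate new from pre-existing abnormalities

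*SAP*

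**What the plan says.** SAP 12.4 (Physical examination) plans three outputs.

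- Pre-treatment summary, by body system within each part and arm. The exam it uses is named in the words "an abnormal result for the latest pre-randomization examination will be summarized by study".
- On-study summary, again by body system. Abnormal results are counted and split into changed and unchanged; the reference point and layout read "from the last examination) will be summarized by study part, treatment group and visit".
- Listing: "All physical examination abnormal results will be listed".

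It specifies no table that sets a subject's pre-treatment result against the on-study result.

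Two neighbouring safety sections do use baseline. For vital signs, 12.3 states: "Vital sign values and changes from baseline will be summarized by study part". For laboratory data, 12.5 plans shift tables from baseline to each later time point.

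In Parts A and B, Exhibits 2 and 3 place the physical exam at Screening, Week 24 and Week 52, at Week 54 for subjects who do not enter Part C, and at early termination. In Part C the exams are at Screening, Week 26 and Week 52, then every six months to Week 182. Section 12 applies its summaries to both Part B and Part C.

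**The concern.** A physical-exam table in a safety report should let a reader see, by arm, how many subjects have an abnormality that they did not have before treatment. When each exam is compared with the one before it, a finding counts as change only once. From the next exam on, if it persists, it sits with the findings that subjects brought into the trial. Week 52 is the last on-treatment exam of the controlled period and the natural place to compare VTS-270 with sham. The Week 52 table cannot make that comparison for findings that first appeared at Week 24. In Part C the mixing continues over more visits, with no concurrent control.

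**Working it through.** No figure in the plan needs reproducing. The check applies the 12.4 rule to the scheduled exams.

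**Which exam is the reference?** Two adjacent sentences in 12.4 use different terms: one names the latest exam before randomization, the next only the last examination. Had the pre-treatment exam been meant, the first term was available. The previous exam is the natural reading, but the SAP does not say so outright.

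**Rule applied to Parts A and B:**

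| First abnormal at | Week 24 cell | Week 52 cell, if unchanged |
|---|---|---|
| Screening | no change | no change |
| Week 24 | change | no change |
| Week 52 | – | change |

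The first two rows share a cell at Week 52. They also share one at Week 54, where that exam is done.

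**Can the split be recovered from the planned tables?** Assume the same subjects attend both visits and that change means newly abnormal. For one body system in one arm, let c24 and n24 be the change and no-change counts at Week 24, m52 the no-change count at Week 52, and k the number new at Week 24 and still abnormal at Week 52. Everyone in m52 was abnormal at Week 24, in either c24 or n24. Hence

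max(0, m52 − n24) ≤ k ≤ min(c24, m52).

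*Hypothetical 1.* The arm has 35 subjects (the planned VTS-270 size, SAP 8.5) and none is abnormal at Screening. Seven become abnormal at Week 24 and stay so. Then c24 = 7, n24 = 0 and m52 = 7. The bounds are max(0, 7 − 0) = 7 and min(7, 7) = 7, so k = 7 can be recovered by comparing visits. Even so, the Week 52 table taken alone reads 0 change, 7 no change, where a baseline reference would read 7 new (7/35 = 20%).

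*Hypothetical 2.* Seven subjects are abnormal at Screening and at Week 24, and seven others become abnormal at Week 24. At Week 52 seven subjects are abnormal, all no change. Then c24 = 7, n24 = 7 and m52 = 7. The bounds are max(0, 7 − 7) = 0 and min(7, 7) = 7. Two histories fit the same planned tables:

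| Shift, pre-dose to Week 52 | New findings resolved | Pre-existing findings resolved |
|---|---|---|
| normal to abnormal | 0 | 7 |
| abnormal to abnormal | 7 | 0 |
| abnormal to normal | 0 | 7 |
| normal to normal | 28 | 21 |
| total | 35 | 35 |

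The pre-treatment table (7 abnormal), the Week 24 table (7 change, 7 no change) and the Week 52 table (0 change, 7 no change) are the same in both columns. Only a shift table separates 0% from 20%.

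Arm totals do not help. The number abnormal at Week 52 equals the number abnormal pre-dose, plus new, minus resolved, so totals show only new minus resolved.

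**The case against.** The strongest reply is that this is a presentation choice in a descriptive table and that the information survives. A persisting finding counts as abnormal at each exam, shows as change when first seen, and is listed. It may also be reported as a treatment-emergent adverse event, and neurological and audiologic evaluations have their own summaries. Sham is a concurrent comparator in Parts A and B. All of this stands. What it leaves is a by-subject split that someone must rebuild from listings.

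Three stronger readings are tempting, and the documents do not support them.

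- *Lasting harms are hidden.* They are not, for the reasons just given. The Week 52 change cell does cover only what arose after Week 24, but earlier findings are in the Week 24 change cell of the same by-visit table. They are spread over visits, not removed.
- *12.4 contradicts SAP 8.2 and 8.3.* Section 8.2 sets a default ("The baseline value for all other study assessments including but not" restricted to a short list of examples) and then allows other definitions where specified. Section 8.3 only says how to calculate a numerical change from baseline. The contrast with 12.3 and 12.5 is an unexplained difference in approach, not a contradiction.
- *On-study percentages are diluted because later exams are shorter.* Exhibit 2 does say "Full physical exam at Screening; abbreviated physical exam at all other visits", and 12.4 says "The denominators will only include subjects" who have the visit being summarized. But the text available does not show which body systems the abbreviated exam covers. Nor does 12.4 say that an unexamined system is counted as not abnormal. A dilution cannot be established or sized from this.

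**Conclusion.** The point holds as a small improvement to a descriptive safety summary. As written, the tables at Week 52, at Week 54 where done, and at successive Part C exams put persisting new findings and pre-existing findings in one no-change cell. The subject-level split by arm cannot in general be read from them. In Parts A and B the effect is limited to findings first seen at Week 24, the only scheduled on-treatment exam before Week 52. More visits are affected in Part C. How many subjects are involved is unknown before the data are seen; the counts of 7 in the working are illustrations. The conclusion rests on reading the reference as the previous exam. If the pre-treatment exam was intended, the wording still needs to say so. No endpoint, test or error rate is affected.

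**What to change.** In SAP 12.4:

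1. State which examination is the reference for change or no change. Do this for Part C too, because the Week 52 visit serves as Part C screening for subjects continuing from Part B.
2. Add a shift table, normal or abnormal, by body system from the last pre-dose exam to each scheduled exam, by study part and treatment group. Restrict it to subjects with that system assessed at both times.

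Keep to two categories. Grading findings as worsened or improved would need severity data that the documents do not show. The existing summary can stay alongside.

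The cost is a small amount of table programming, in the format already planned for laboratory data. It assumes that normal/abnormal results are held by body system, as the summaries already planned in 12.4 imply. No new data collection is involved.

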12.5. Laboratory data

Exhibit 2 – Exhibit 7 displays the timing of laboratory tests. Clinical laboratory values and

changes from baseline will be summarized by study part, treatment group and time point.

Laboratory data will be summarized by presenting shift tables from baseline to each post-

baseline time point. Figures may be used if appropriate.

12.6.Audiologic evaluation

Audiologic evaluations were used as exploratory clinical endpoints as well as additional safety

measurements assessing ototoxicity. The audiologic evaluations performed over the course of

the study included: behavioral assessment of pure tones and speech measures (threshold and

word discrimination), tympanometry, otoacoustic emissions, and ABR. Pure tone assessment

(Air Conduction and Bone Conduction) will be summarized as it best captures possible

ototoxicity.

Air conduction (AC) was tested at the following frequencies: 250 Hz, 500 Hz, 1000 Hz,

2000 Hz, 3000 Hz, 4000 Hz, 6000 Hz, and 8000 Hz. Bone conduction (BC) was tested at the

following frequencies: 250 Hz, 500 Hz, 1000 Hz, 2000 Hz, and 4000 Hz. Descriptive statistics

of hearing thresholds in decibels will be presented by study part, treatment group, conduction

type, visit, frequency and ear.

Pure tone averaging was done for both AC and BC across low frequencies of 500 Hz, 1000 Hz,

and 2000 Hz. Pure tone averaging will also be done for AC at high frequencies of 4000 Hz,

6000 Hz, and 8000 Hz. If at least two non-missing thresholds are obtained per conduction type

and ear, the pure tone average (PTA) for AC and the bone conduction average (BCA) for BC

will be calculated by adding up the threshold levels in decibels (dB), and then dividing the

sum by the number of thresholds obtained. PTA and BCA will be summarized by study part,

treatment group, visit and ear.

CONFIDENTIAL

August 27, 2018

Page 44

A diagnostic ABR was tested at the following frequencies: 500 Hz, 1000 Hz, 2000 Hz, and 4000 Hz. Descriptive statistics of hearing thresholds in decibels will be presented by study part, treatment group, visit, frequency and ear.

When conducting the PTA and ABR, the sites recorded the type of hearing impairment and hearing impairment severity. Hearing impairment severity was categorized as follows (more than one could apply to a subject at each assessment).

- Normal hearing (-10 to 15 dB)
- Slight hearing impairment (16 to 25 dB)
- Mild hearing impairment (26 to 40 dB)
- Moderate hearing impairment (41 to 55 dB)
- Moderate-severe hearing impairment (56 to 70dB)
- Severe hearing impairment (71 to 90 dB)
- Profound hearing impairment (91 + dB)
- High Frequency Hearing Impairment (defined as an impairment at 4k and above)

Hearing impairment severity will be summarized for both PTA and ABR by study part, treatment group and visit.

All audiometry assessments will be listed by subject.

A sensitivity analysis will be performed to address the impact that the known risk of ototoxicity from study drug may have on the adequacy of blinding. The concern comes if the site staff performing the NPC-SS assessment notices over the course of the study that the subject experiences clinical hearing impairment. Will the knowledge of hearing impairment cause the NPC-SS assessment to be knowingly or unknowingly biased? Because the audiologic evaluation results are kept blinded from the site staff performing the NPC-SS assessment, we will instead use the reporting of hearing impairment as an adverse event (by the blinded AE rater) due to clinical manifestation as a marker of hearing impairment in this analysis. A standard MedDRA query for hearing impairment will be used to identify these terms. The recommendation for hearing aides to a subject will also be included in this

analysis. The site staff member performing the NPC-SS assessment also is blinded to the AEs

that are recorded for the subject.

In order to assess whether there was an impact due to unblinding, the co-primary efficacy

NPC-SS composite endpoint analysis will be repeated (a nonparametric ANCOVA, with

treatment group, study part, and baseline included in the model), but will also include a

variable indicating the recording of hearing impairment (AE or recommendation for hearing

aid) and a hearing impairment by treatment group interaction variable in the model. A

significant hearing impairment by treatment group interaction variable (two-sided α =0.05 level

of significance) will provide evidence that an unblinding bias has occurred.

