6.4. Safety population

The safety population will consist of all randomized subjects who receive at least one dose of

VTS-270 or sham control. The safety population will be analyzed by the actual treatment

group.

6.5.Part C open-label population

The Part C open-label population will consists of all subjects who receive at least one dose of

VTS-270 during Part C.

6.6.Device safety and tolerability substudy population

The device safety and tolerability substudy population will consist of all subjects who receive

at least one dose of VTS-270 via the IT access device in Part C.

August 27, 2018

Page 22

7. Blinded data review meeting

A blinded data review meeting will be held prior to locking the database and breaking the

blind. The purpose is to assign subjects to populations based on the above definitions.

Allocation of subjects to populations and all decisions made during this meeting will be

documented in the meeting minutes.

The following listings will be provided for the meeting and will follow definitions of the ITT,

mITT and safety populations:

• eligibility of all subjects

demographic and other baseline data

medical history

prior and concomitant medications

post-treatment efficacy assessments completed or not

To define the PP population, a listing of protocol deviations will be provided.

Missing data, visit windows, and subject withdrawals may be reviewed. Further ad hoc

listings may be provided as required.

No further definition of populations will be made after the blind data review meeting.

8. General conventions and statistical considerations

Descriptive and inferential statistics will be used to summarize results. Standard descriptive

statistics, such as tabulations by clinically relevant discretizations, the mean, median, standard

deviation, quartiles, minimum, and maximum, will be calculated for continuous variables. For

discrete variables, descriptive analyses will be based on numbers of subjects and related

percentages.

In order to control for interpretability issues that could arise from pooling Part A subjects

(randomized 3:1 treatment: sham) with the Part B subjects (randomized 2:1 treatment: sham),

and to keep the integrity of the randomization, all table presentations will display results in

two ways. First, the results will be presented by overall treatment group (one column per treatment group), similar to that shown below:

Overall	Overall		
Sham	Treatment	Total	
(N=X)	(N=X)	(N=XX)	

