• Subjects randomized in Part B, miglustat use -, NPC-SS total score < 20

8.8.Safety parameters

All safety summaries will present data by study part. Summaries will present adverse

events, including those related to the study treatment and administration procedure. Serious

adverse events will be summarized similarly and include narratives as well. Clinical

laboratory, vital sign and ECG values and changes from baseline will be summarized by

treatment group and time point. Physical examination abnormal results will be listed and

summarized. Results of several audiologic evaluations and ABR will be summarized and

presented.

In addition to the above assessments, the following safety evaluations will be conducted for

the device safety and tolerability substudy in Part C:

Wound check, examination of port site and catheter track at access port infusion visits

• Intracranial pressure (ICP) via LP

9. Study population summaries

9.1.Enrollment

Enrollment will be summarized by treatment group. A table will present the number and

percentages of subjects in each stratum by treatment group. A listing of screen fail subjects

with reason for screen fail will be provided.

9.2.Subject disposition

The disposition of subjects (number randomized but did not receive study drug, number

randomized and received all study drug procedures, number randomized but who did not

receive all study drug procedures) will be tabulated by study part and treatment group and

presented in a CONSORT diagram. All possible reasons for not receiving all study drug

procedures will be summarized by study part and treatment group.

Listings will present time to and reason for discontinuation or withdrawal by study part,

treatment group and subject.

The analysis population table will summarize the number and percent of subjects in the

following populations:

ITT

mITT (primary population for efficacy assessments)

Per Protocol

Safety Population.

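### SAP 12.6 plans no change from baseline and no VTS-270 minus sham difference with a confidence interval for hearing thresholds or pure tone averages, so the size of any hearing loss in dB is not estimated

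*SAP*

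**What the plan says.** **Audiology.** SAP 12.6 singles out pure tone assessment as the best indicator of possible ototoxicity. It then plans the following:
- Air and bone conduction: descriptive statistics "of hearing thresholds in decibels will be presented by study part, treatment group, conduction" type, visit, frequency and ear.
- Averages: "PTA and BCA will be summarized by study part", treatment group, visit and ear. Air conduction PTA is formed at low (500, 1000, 2000 Hz) and high (4000, 6000, 8000 Hz) frequencies and needs at least two of the three thresholds.
- Diagnostic ABR, tested at 500 to 4000 Hz: "Descriptive statistics of hearing thresholds in decibels will be presented by study part, treatment group, visit, frequency and ear".
- Hearing severity categories, which are not mutually exclusive, by visit and treatment group.

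The same section refers to the "known risk of ototoxicity from study drug may have on the adequacy of blinding".

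**Other safety data.** SAP 12.3: "Vital sign values and changes from baseline will be summarized by study part", treatment group and time point. SAP 12.5, for laboratory values: "changes from baseline will be summarized by study part, treatment group and time point", with shift tables as well. SAP 8.8 plans changes from baseline for laboratory, vital sign and ECG values; for hearing it says only "Results of several audiologic evaluations and ABR will be summarized and" presented.

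**Hearing measures elsewhere in the SAP.** Section 12.1.1 grades objective hearing events at every post-baseline audiologic evaluation, mainly on threshold shift, and 12.1.2 tabulates hearing events by treatment group as events of special interest. Section 11.4 tests change from baseline to Week 52 in each of the nine NPC-SS domains against sham with methods like the co-primary analysis, which uses ranks. Hearing is one of the nine and is scored mainly from PTA bands (Table A1).

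**The concern.** Safety and tolerability compared with sham is a Part B objective, and hearing loss is the toxicity that the SAP itself names. The measure that it regards as most informative gets a weaker analysis than blood pressure or laboratory values: no reference to the subject's own baseline, and no estimate of the difference between arms.

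The eligibility criteria set no hearing limit, and the NPC-SS hearing item runs from normal to profound. The documents therefore allow wide differences in hearing at entry, though they give no data on the actual spread. With a sham arm of about 16 subjects, means of raw thresholds by visit would carry a good part of any chance imbalance at entry.

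The key secondary NPC-SS total leaves out the hearing domain and the ABR modifier. That makes a direct estimate of hearing harm more useful for weighing benefit against risk. Without it, a reader of the results could say how many subjects crossed a grade in each arm, but not how many decibels were lost relative to sham or how precisely that is known.

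**Working it through.** **1. Do the other hearing measures give a dB effect?**
- *Graded events.* On audiometry, grades 1 and 2 need a shift above 20 dB; grade 3 uses the same cut from 3 kHz upward, together with need-for-intervention criteria; grade 4 uses an absolute threshold. The ABR scale starts above 10 dB. On audiometry a 20 dB shift reaches no shift-based grade, while shifts of 25 dB and 60 dB confined to 8 kHz in one ear meet the same grade 1 shift criterion. The result is a count by category.
- *NPC-SS hearing domain.* PTA from 16 to 44 dB is a single score, so a loss of 44 - 16 = 28 dB can register as no change. High-frequency loss with PTA at or below 15 dB scores 1 whatever its size. The test is on ranks.
- *Severity categories.* They are reported by visit, can overlap, and have no planned shift table.

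All are informative about hearing, but none yields a mean dB change or a difference from sham in dB.

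**2. Could the estimate be made from the planned data?** Yes. Audiologic testing is scheduled at screening, Day 0, Weeks 8, 16, 24, 32, 40, 46 and 52, and early termination, with Weeks 2, 4 and 6 in Part A only. SAP 8.2 defines baseline for these data as the last non-missing value before first dose, and 8.3 defines change.

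**3. What would baseline adjustment gain?** The plan has no figure for hearing to reproduce; its only power calculation concerns the NPC-SS composite. The inputs below are for illustration.
- Sample size: SAP 8.5 gives 54 randomized but no split. I assume 37 and 17 (planned 35 and 16, with the three extra subjects divided 2:1).
- Threshold SD: assumed 20 dB at both times (range 15-25).
- Correlation r between baseline and Week 52: assumed 0.8 (range 0.7-0.9).

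Half-width of the 95% CI = t(0.975, 52) × SD × √(1/37 + 1/17) × k, where k = 1 for raw Week 52 values, √(2(1 - r)) for change, and √(1 - r²) for baseline adjustment.

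√(1/37 + 1/17) = √(0.0270 + 0.0588) = 0.293, and t = 2.007. For SD 20 the common factor is 2.007 × 20 × 0.293 = 11.8 dB.

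| Analysis | r = 0.7 | r = 0.8 | r = 0.9 |
|---|---|---|---|
| Raw Week 52 | 11.8 | 11.8 | 11.8 |
| Change from baseline | 9.1 | 7.4 | 5.3 |
| Baseline-adjusted | 8.4 | 7.1 | 5.1 |
| Adjusted, narrower than raw by | 29% | 40% | 56% |

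The percentage is 1 - √(1 - r²) and does not depend on the SD. At r = 0.8, an SD of 15 gives 8.8 dB raw and 5.3 adjusted; an SD of 25 gives 14.7 and 8.8. With the planned 35 versus 16, SD 20 and r = 0.8, the figures are 12.1 and 7.3 dB.

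**4. How much chance imbalance carries over?** The baseline difference between arms has SD 20 × 0.293 = 5.9 dB. With equal SDs, a fraction r of it passes on average into the raw Week 52 comparison: 0.8 × 5.9 = 4.7 dB (4.1 to 5.3 dB for r = 0.7 to 0.9).

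**The case against.** A reader might infer that hearing is summarised only as raw values, with no comparison with sham. The documents do not support that. Graded hearing events based on threshold shift are tabulated by arm. Change in the PTA-based hearing domain is formally tested against sham, as is total NPC-SS with hearing and ABR included. SAP section 8 states: "First, the results will be presented by overall treatment group (one column per treatment group), similar to that shown below"; sham thus stands beside treatment in every table, and the overall template has a p-value column. The by-visit tables would also show pre-dose values, so an approximate mean change per arm could be read off, and all audiometry is listed by subject. These points stand. What they do not supply is a within-subject change in dB or its precision, and 12.6 names no test or estimate to fill the p-value column.

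The contrast with vital signs and laboratory data supports only the change-from-baseline tables, because no adjusted difference or interval is planned there either. This is fair. The case for the between-arm estimate rests instead on the objective of comparing safety with sham and on this being the named risk.

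The SD, correlation and 37/17 split are not in the documents, and the 40% is simply the consequence of r = 0.8. This also stands; the figures illustrate and do not predict.

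Finally, the remedy does not remove dependence on who can be tested. Subjects assessed only by ABR have thresholds up to 4 kHz and cannot form a high-frequency PTA. That limitation is real and should be reported with the result.

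**Conclusion.** The point holds in this form: SAP 12.6 plans no change from baseline and no between-arm difference with a confidence interval for dB thresholds, PTA or BCA. Hearing change against sham is covered only by shift-graded events and the ordinal, rank-tested hearing domain. The frequency of graded loss by arm will be known; its size in dB will not.

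It would go too far to say that the risk is not quantified at all, or that the whole of a chance baseline imbalance enters the raw comparison: on average a fraction r does.

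Under the assumptions stated, baseline adjustment would narrow the interval for the arm difference from about ±11.8 dB to ±7.1 dB, about 40% (29-56% for r from 0.7 to 0.9). The textual gap does not depend on those assumptions. The change should be made, but it does not affect the efficacy conclusions.

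**What to change.** In SAP 12.6:
1. Add same-ear, same-frequency change from baseline, by visit and arm, for air and bone conduction thresholds and for low- and high-frequency PTA. Do the same for diagnostic ABR thresholds in subjects tested that way, at the visits where ABR is done.
2. Report the VTS-270 minus sham difference in Week 52 high-frequency PTA change with a 95% CI, adjusted for baseline and study part. Label it a descriptive safety estimate, outside the efficacy testing hierarchy.
3. Give the number of subjects in each arm who contribute to that estimate.

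The cost is a few extra tables and one model from data already collected; no visit or test is added. The downside is that subjects without matched baseline and Week 52 behavioural audiometry, including those tested only by ABR, do not contribute to the high-frequency PTA estimate. The graded events and the ABR change tables should be read alongside it.
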